6.1 Study Agent(s) and Control Description

The SCFA oral supplement is an over the counter, non-FDA approved capsule containing butyrate. It is marketed as a dietary supplement. Butyrate and other SCFA are produced normally by gut commensal microbiota and are present at varying levels in the guts of all humans. Participants will self-administer the oral SCFA supplement three times daily, with meals for up to 2 months. This is an open label pilot proof of concept study therefore no placebo will be utilized.

6.1.1 Acquisition

The SCFA supplement will be acquired by purchase from the manufacturer and shipped to the investigator. All efforts will be made to acquire same lot number of the product.

6.1.2 Formulation, Appearance, Packaging, and Labeling

We will use a butyrate supplement from Biotics Research® or Bodybio, Inc. which is commercially marketed. The supplement comes in a capsule form that contains 1033 mg butyric acid (as calcium and magnesium butyrate), Vitamin A, Panthenic acid, ethyl vanillin (flavoring) and cellulose (capsule shell). It is gluten and dairy free. This product is commercially available for human use in the form, route and dose planned for this pilot study.

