Objectives	
Primary objective:
 
 To determine whether oral SCFA supplementation in RA inadequate responders induces changes in the gut microbiome composition 
Key secondary objectives:
 
 To determine whether oral SCFA supplementation in RA inadequate responders induces changes in the peripheral Treg population To measure changes in adaptive immune response over time with oral supplementation of SCFA To measure changes in serum and fecal SCFA concentration with oral supplementation of SCFA To measure MTX and its metabolites in fecal and urine samples after oral SCFA supplementation To measure changes in the gut microbiome composition in methotrexate inadequate responders who do not want to take oral SCFA supplements. To measure changes in the gut microbiome composition in methotrexate inadequate responders after they initiate next line therapy (as prescribed by their treating physician)
Methodology	Open label pilot proof of concept study
Endpoint	
Primary endpoint:
 
 The primary endpoint will be an increase in microbiome alpha diversity from baseline visit 1 to visit 2 after SCFA supplementation. 
Important secondary endpoints:
 
 We will determine the changes to serum and fecal SCFA after SCFA supplementation and determine the changes in adaptive immune response including peripheral Treg cell populations.
Study Duration	Up to 4 years
Participant Duration	Up to 14 months

[figure not shown]
Duration of IP administration	Up to 2 months
Population	Any Rheumatoid Arthritis patient who is an inadequate responder to current RA treatment: 
• Age 18 years and above• Subjects not excluded based on gender, race or ethnicity, general health status, or geographic location
Study Sites	NYU Langone Health inpatient and outpatient sites, Bellevue Hospital
Number of participants	65 participants
Description of Study Agent/Procedure	Study agent is an oral SCFA supplement containing butyrate. It will be taken orally 1000mg three times a day with meals.
Key Procedures	Blood draws Stool collection Urine collection

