2.2.3 Dose Rationale

Butyrate 1000 mg three times daily will be used in this study. This dose was based on doses found in the literature and over the counter general use guidelines that ranged from 1000mg – 6000 mg daily^{8,10,11}. In our ongoing study in NORA patients, the proposed dosing regimen is feasible, tolerable and promotes changes in gut microbiome diversity (unpublished data).

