4.1 Description of Study Design

This study is a pilot proof of concept, open label study of the effects of oral SCFA supplementation in RA patients with an inadequate response to MTX. We will be enrolling all patients with RA who fulfill inclusion/exclusion criteria. This will be a single center study based in the NYU Langone hospitals and clinics as well as Bellevue Hospital which falls under its umbrella. Oral butyrate will be taken at 1000 mg three times daily with meals by RA patients who have active disease and are currently taking MTX at prescriber's recommended dose. There will be no dose escalation of the study supplement.

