6.1.5 Dosing and Administration

The SCFA oral supplement should be stored in a dry place at room temperature. Participants will take two capsules by mouth three times daily with meals. If a participant misses a dose, the dose can be taken within 3 hours of the missed dose with or without food, otherwise participant can just wait until next dose. Do not double up on dose if missed previous dose.

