6.1.7 Starting Dose and Dose Escalation Schedule

Participants will take two capsules by mouth three times daily with meals. There will not be any dose escalation.

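### The stated dose of 1000 mg three times daily does not match the stated capsule content and capsule count; read plainly they give about twice that dose, and the content per capsule is not given for each product

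*Combined protocol and SAP*

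**What the plan says.** Three places give the dose in milligrams. The Protocol Summary, in the row describing the study agent, says "It will be taken orally 1000mg three times a day with meals". Section 2.2.3 (Dose Rationale) says "Butyrate 1000 mg three times daily will be used in this study", and section 4.1 says "Oral butyrate will be taken at 1000 mg three times daily with meals".

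Section 2.2.3 supports the choice by published doses and "over the counter general use guidelines that ranged from 1000mg" up to 6000 mg daily. It adds that the regimen has been feasible and tolerable in an ongoing study in new-onset RA.

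Section 6.1.2 names two possible manufacturers and gives one composition: "The supplement comes in a capsule form that contains 1033 mg butyric acid (as calcium and magnesium butyrate", with further ingredients. Section 6.2 allows the second manufacturer's product to be bought if the first has production delays.

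The instruction in capsules appears twice. Section 6.1.5 says "Participants will take two capsules by mouth three times daily with meals", and section 6.1.7 says "Participants will take two capsules by mouth three times daily with meals. There will not be any dose escalation".

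Section 6.1.10 checks compliance by counting leftover capsules. Section 6.1.9 calls a participant evaluable after at least two weeks of supplementation.

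**The concern.** Milligrams per capsule times capsules per dose should equal the stated milligrams per dose. On the plain wording it does not, and the gap is about two-fold. The milligram dose appears three times and the two-capsule instruction twice, so one typing slip does not obviously explain it.

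The dose is the intervention. As the text stands, a reader cannot establish how much butyrate participants are meant to take, so the result could not be replicated or set against other studies by dose. The justification in 2.2.3 covers one reading and not the other.

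The ambiguity also bears on safety. Section 2.2.2 reports no clinical research data on this product, and section 2.4.1 attributes the expected gastrointestinal effects to taking concentrated fatty acids. It can reach participants too: section 6.2 puts dosing instructions on the bottle, and section 7.8 promises brand and dosage information to those who wish to continue on their own.

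**Working it through.** **Inputs**
- Stated dose: 1000 mg, three times daily (Protocol Summary, 2.2.3, 4.1).
- Capsule content: 1033 mg butyric acid (6.1.2). The text does not say in so many words whether this is per capsule or per serving.
- Capsules per dose: 2, three times daily (6.1.5, 6.1.7).
- Supporting range: 1000 to 6000 mg/day (2.2.3).

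**Formulas**
- mg per dose = capsules per dose x mg per capsule
- mg per day = 3 x mg per dose

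**Step 1. The stated dose.** 3 x 1000 = 3000 mg/day, inside the 1000 to 6000 range.

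**Step 2. Can the capsule figures reproduce it?** Two capsules per dose give 1000 mg only if each holds 1000 / 2 = 500 mg. No section gives such a content.

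**Step 3. The two readings of 1033 mg, with two capsules per dose**

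| Reading of 6.1.2 | mg per capsule | mg per dose | mg per day | Ratio to 3000 | Against 6000 mg/day |
|---|---|---|---|---|---|
| 1033 mg in one capsule (plain reading) | 1033 | 2 x 1033 = 2066 | 3 x 2066 = 6198 | 6198 / 3000 = 2.07 | above by 198 mg; 198 / 6000 = 3.3% |
| 1033 mg in two capsules (not stated anywhere) | 1033 / 2 = 516.5 | 1033 | 3 x 1033 = 3099 | 3099 / 3000 = 1.03 | below |

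**Step 4. A third combination.** One 1033 mg capsule per dose would also give 3 x 1033 = 3099 mg/day, but this contradicts the two-capsule instruction. So two different departures from the plain wording lead to nearly the stated dose. One changes the meaning of 6.1.2; the other changes 6.1.5 and 6.1.7. Nothing in the document chooses between them, or between either of them and the plain reading.

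**Step 5. Two products.** The calculation uses one content figure because only one is given. If the two products differ in content per capsule, the same instruction yields different doses. The size of any such difference cannot be derived from the document.

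**The case against.** The strongest reply is that the sections may be compatible. Section 6.1.2 describes a capsule form and does not say that each capsule holds 1033 mg. If 1033 mg is the content of a two-capsule dose, every section agrees to within 3.3% (3099 against 3000 mg/day) and the total lies well inside the cited range. This stands as a possibility, so it would be too strong to say that the sections cannot all be right. It does not remove the point: the per-serving reading is nowhere stated, the plain reading is per capsule, and neither reading is given for each product.

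Two stronger inferences are tempting and should not be drawn.

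- **Adherence.** A reader might infer that someone taking one capsule per dose would be fully adherent to the milligram dose, yet would score 50% on the capsule count (3 x 30 = 90 of 6 x 30 = 180 capsules over 30 days). But the only capsule instruction in the protocol is six per day, so that is the documented expected count whatever the strength. Section 6.1.10 sets no adherence threshold, and section 6.1.9 defines evaluable participants by duration.
- **The effect size of 0.63.** A reader might infer that the preliminary effect behind the sample size no longer applies. Section 2.2.3 says that the proposed regimen is the one in use in the new-onset RA study, and nothing shows that the regimens differ. Unclear milligram wording does not by itself break that link.

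It can also be said that traceability is partly in place. Section 6.1.1 aims for a single lot, and section 6.2 keeps dispensing records by bottle number and puts the supplement name on the label. That is fair. What is missing is an explicit record of which product each participant received.

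**Conclusion.** The dosing text is inconsistent as written and must be reconciled. On the plain reading the capsule instruction delivers 6198 mg/day against a stated 3000 mg/day, a ratio of 2.07, and exceeds the upper end of the protocol's own justifying range by 3.3%.

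These figures rest on one assumption: that 1033 mg is the content of one capsule. If it is the content of two, the discrepancy shrinks to 3.3% of the stated dose and the range is respected. The document does not settle which is meant, and no view is taken here on which dose is right.

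The consequence lies in the definition, justification and reporting of the intervention. The primary analysis is a within-participant comparison of Shannon diversity, and no milligram figure enters the sample-size calculation in 9.1 and 9.2. The test and the target of 25 evaluable participants are therefore not directly affected.

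**What to change.** 1. State the butyric acid content per capsule, separately for each of the two products, in 6.1.2.
2. Reconcile the Protocol Summary, 2.2.3, 4.1, 6.1.2, 6.1.5 and 6.1.7, so that mg per capsule times capsules per dose equals the stated mg per dose for each product.
3. Check the reconciled daily total against the range in 2.2.3, and revise the rationale if the total falls outside it.
4. Make the dosing instructions on the bottle (6.2) consistent with the reconciled text.
5. Record in the study database which product each participant received.

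The cost is a check of the two product labels, amendment wording and one added data field. A correction to the bottle label or consent form is needed only if those carry a figure that changes. That cannot be judged here, because the bottle text is not shown and the consent pages are not among the material reviewed. The primary analysis and sample size need no change.

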6.1.3 Product Storage and Stability

As per the manufacturer's recommendations, the product should be stored in a cool, dry area. According to manufacturer, the supplement expires approximately three years from manufacture date. We will plan to use supplement within at most one year from manufacture date.

6.1.4 Preparation

The SCFA oral supplement does not need any additional preparation prior to ingestion.

6.1.5 Dosing and Administration

The SCFA oral supplement should be stored in a dry place at room temperature. Participants will take two capsules by mouth three times daily with meals. If a participant misses a dose, the dose can be taken within 3 hours of the missed dose with or without food, otherwise participant can just wait until next dose. Do not double up on dose if missed previous dose.

6.1.6 Route of Administration

Oral

6.1.7 Starting Dose and Dose Escalation Schedule

Participants will take two capsules by mouth three times daily with meals. There will not be any dose escalation.

6.1.8 Dose Adjustments/Modifications/Delays

If a participant misses a dose, the dose can be taken within 3 hours of the missed dose with or without food, otherwise participant can just wait until next dose. Do not double up on dose if missed previous dose.

6.1.9 Duration of Therapy

Participants will self-administer the oral SCFA supplement three times daily, with meals for up to 2 months. The minimum duration necessary for an “evaluable” participant will be 2 weeks of SCFA supplementation.

6.1.10 Tracking of Dose

Participants will be given up to a 6-week supply at a time in an appropriate container. Patients will be asked to bring the container with them at follow up visits such that study coordinators can count remaining capsules to determine compliance. Participants will be called not more than on a weekly basis to discuss compliance to the study supplement for reinforcement.

6.1.11 Device Specific Considerations

Not applicable.

6.2 Study Agent Accountability Procedures

Biotics Research Butyric Cal-Mag supplements will be purchased from Agape Nutrition (agapenutrition.com; [name]). Alternatively, we can also procure Bodybio Calcium Magnesium Butyrate from Bodybio.com contingent on production lags by Biotics Research. The supplement bottles will be stored between 15° to 30° C at the NYU Langone Orthopedic Center, in a locked drawer in a locked room with a digital lock. Only those study team members delegated to dispense the supplements will have access.

The study compound will be labeled according to local regulatory requirements. Once dispensed to a subject, bottle labels will contain the following information:

- Bottle ID number
- Name of supplement
- Principal Investigator name
- Study team address and phone contact
- Date of dispensation
- Participant name/study ID
- Dosing instructions
- Date of expiration, if applicable

Records will be maintained by the study team indicating the receipt and dispensation of all supplies, including subject ID, date of dispensation, and bottle ID number.

At the conclusion of their participation, subjects will have the option to return any remaining product or dispose of the supplement on their own after end of the study.

7 Study Procedures and Schedule

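### Two brands share one unattributed composition statement, and the stated mg dose, the capsule content and the capsule count do not clearly agree for either brand

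*Combined protocol and SAP*

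**What the plan says.** - **Brands.** Section 6.1.2: "We will use a butyrate supplement from Biotics Research® or Bodybio, Inc. which is commercially marketed". Section 6.2 makes the second brand a contingency: "Alternatively, we can also procure Bodybio Calcium Magnesium Butyrate from Bodybio.com contingent on production lags by Biotics Research". Section 2.2.2 says there are no clinical data to date on the product from either source.
- **Composition.** Section 6.1.2 then describes one product: "The supplement comes in a capsule form that contains 1033 mg butyric acid (as calcium and magnesium butyrate), Vitamin A, Panthenic acid, ethyl vanillin". It assigns this to neither brand.
- **Dose in mg.** The Protocol Summary and sections 2.2.3 and 4.1 give 1000 mg three times daily. Section 2.2.3 supports this with a range of 1000 to 6000 mg per day from the literature and over-the-counter guidelines.
- **Dose in capsules.** Sections 6.1.5 and 6.1.7 give two capsules three times daily, with no distinction by brand.
- **Lots.** Section 6.1.1: "All efforts will be made to acquire same lot number of the product". Section 6.1.3: "We will plan to use supplement within at most one year from manufacture date". The Protocol Summary puts study duration at no more than 4 years; no accrual period is given.
- **Records.** Section 6.2 requires records of supplies received and dispensed, "including subject ID, date of dispensation, and bottle ID number". The bottle label carries the supplement name and bottle ID, but no lot.
- **Adherence.** Section 6.1.10: "Participants will be given up to a 6-week supply at a time in an appropriate container". Compliance comes from counting the capsules left.
- **Analysis.** Section 9 mentions neither brand nor lot.

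**The concern.** A capsule-count instruction gives every participant the same exposure only if each capsule holds the same amount. The protocol does not say that it does. Even for one brand, the mg dose, the composition and the capsule count fit together under one reading and differ by a factor of about two under the other.

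The study has no placebo arm, and its primary result is a within-participant change in Shannon index among about 25 supplement takers. Interpreting that change, and above all a null result, depends on knowing what was taken. A later study would also need to know which daily amount this one tested.

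A second, smaller matter is traceability. If lot and quantity are not captured at dispensing, they may not be recoverable later, and a count of leftover capsules yields an adherence figure only when the number dispensed is known.

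**Working it through.** **1. Dose arithmetic.** Inputs: 1033 mg (6.1.2); two capsules, three times daily (6.1.5, 6.1.7); 1000 mg three times daily (Protocol Summary, 2.2.3, 4.1).

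| Reading of 1033 mg | Per dose | Per day | Stated per day | Ratio |
|---|---|---|---|---|
| Per capsule | 2 × 1033 = 2066 mg | 3 × 2066 = 6198 mg | 3 × 1000 = 3000 mg | 2.07 |
| Per two-capsule serving (516.5 mg per capsule) | 1033 mg | 3 × 1033 = 3099 mg | 3000 mg | 1.03 |

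On the first reading the daily amount also exceeds the top of the range in 2.2.3 by 6198 − 6000 = 198 mg. On the second it is 99 mg above the stated daily dose, which could be rounding. The text does not choose between them, and for the second brand no content figure can be assigned at all.

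**2. The plan's sample size.** This reproduces. Using the noncentral t with n multiplied by 3/π for the signed-rank test, n = 25 gives an effective n of 23.87 and noncentrality 0.60 × √23.87 = 2.93, so power is 0.801. For n = 23 and d = 0.63, power is 0.804. Simulation of the exact test gives 0.802 and 0.800. There is no error here.

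**3. What unequal products would cost (illustration only).** Suppose a share p of takers receives the second brand, with a fraction r of the planned effect. The mean effect is 0.60 × [1 − p(1 − r)]. Neither p nor r is in the documents. Power below is simulated with n = 25.

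| r | p | Mean effect | Power |
|---|---|---|---|
| 1 | any | 0.60 | about 80% |
| 0.8 | 20% / 40% | 0.576 / 0.552 | about 77% / 73% |
| 0.5 | 20% / 40% / 50% | 0.54 / 0.48 / 0.45 | about 70% / 61% / 56% |
| 0 | 20% / 40% | 0.48 / 0.36 | about 60% / 35% |

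**4. What a by-brand comparison could show.** With 25 takers and brand fully recorded, the difference detectable at 80% power is (1.96 + 0.84) × √(1/n₁ + 1/n₂), in SDs of the paired change.

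| Split | Detectable difference | Power for 0.6 SD |
|---|---|---|
| 12 v 13 | 1.12 | 32% |
| 8 v 17 | 1.20 | 29% |
| 5 v 20 | 1.40 | 22% |

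**5. Lots.** Minimum lots = dosing span ÷ usable months per lot, rounded up. If the last participant completes 14 months within 48, accrual is at most 48 − 14 = 34 months and dosing spans 34 + 2 = 36 months. That needs 36/12 = 3 lots on fresh stock, 36/9 = 4 if stock arrives 3 months old and 36/6 = 6 if it arrives 6 months old. One lot suffices if accrual plus 2 months of dosing fits the usable life, so accrual can run to 10, 7 or 4 months respectively. Accrual lengths and stock ages are assumptions.

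**6. Capsule counts (illustration).** A six-week supply at six capsules a day is 6 × 42 = 252. If 72 remain at day 30, then 252 − 72 = 180 were taken, against 6 × 30 = 180 expected. Had five weeks' supply (6 × 35 = 210) been given, the same 72 would mean 138 taken, or 77%.

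**The case against.** The case on the other side is that this is documentation detail in an open-label pilot of an over-the-counter product. Both products are described as calcium and magnesium butyrate, the second is only a contingency, and the serving reading makes the doses agree to within 3%. Serum and fecal SCFA measurements (4.2.2) give some check on delivery. All of that is fair. It still leaves the content per capsule unstated, and no text adopts the serving reading.

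Four stronger inferences are tempting, and the documents do not support them:

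- **That a single lot is impossible.** The same-lot wording is best effort, the one-year limit is a plan, 4 years is a maximum, and no accrual period is given. A single lot is unlikely only if dosing spans more than a year.
- **That the records hide any product effect.** The list of record items is open-ended, and the label carries supplement name and bottle ID. The two products have different names in 6.2, so brand is probably recoverable. Lot and quantity are unnamed, and so not assured, but they are not excluded.
- **That a participant who changes brand contaminates the primary endpoint.** The schedule in 7.3 dispenses at visit 1 and optionally at visit 2, and the endpoint closes at visit 2. Such a change could reach only the later, optional visits. Mixing of brands between participants remains possible.
- **That the primary result averages unequal products at a known cost in power.** Nothing shows that the brands differ; the plan merely does not show that they match. The power losses depend on invented shares and effect ratios, and equal products would lose nothing.

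**Conclusion.** The concern holds for the dose statements. The protocol allows two brands, gives one composition assigned to neither, and doses both by the same count. Its mg dose matches that count only if 1033 mg refers to two capsules. Otherwise the daily amount is 6198 mg against 3000 mg, a ratio of 2.07. This rests on the documents' own figures and needs no assumption. The trial relies on that figure, and the text is easily corrected.

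Traceability is a lesser gap: brand is probably recoverable, while lot and quantity are not assured. The sample size of 25 is sound as calculated. The power losses are hypothetical and should not be cited as an expected effect, and any comparison by brand is descriptive, with 22% to 32% power for a difference as large as the planned 0.6 SD.

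**What to change.** **Main change.** In 6.1.2, state butyric acid content per capsule separately for each brand. Then reconcile the mg dose (Protocol Summary, 2.2.3, 4.1), the composition (6.1.2) and the capsule-count instruction (6.1.5, 6.1.7) brand by brand. Which amount is right is for the sponsor. The cost is a few lines of text.

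**Low-cost additions.**
- In 6.2, name brand, lot, and capsules dispensed and returned among the recorded items. This adds a few fields to the dispensing log and REDCap.
- In section 9, add one table giving the visit 1 to visit 2 Shannon change by brand, labelled descriptive, with no test.
- In 6.1.1, acknowledge that more than one lot may be used if dosing runs beyond a year.

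Whether a participant should stay on one brand is for the sponsor to decide. Such a rule could interrupt that participant's supply, and it would not alter the primary endpoint.
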